- b. Subjects who remain eligible for re-treatment will continue in the re-treatment period for a total of 96 months (± 14 days) from the time of the baseline visit in study B1801023.
- c. Subjects in the re-treatment period who withdraw from investigational product for any reason before completion of the Month 96 visit are required to complete the retreatment early withdrawal visit at the study site. At that time, the subject will be asked to participate in the observational period. Subjects may not enter the withdrawal/re-treatment period more than once during the study.
- d. The follow-up visit will only completed for subjects who are receiving investigational product in either the active treatment period or the re-treatment period approximately 96 months after the baseline visit in study B1801023 and will occur at the study site 30 days (± 7 days) after the Month 96 visit.
- e. Subjects who receive at least 1 dose of investigational product in the re-treatment period of study B1801023 and withdraw from the re-treatment period before completion of the month 96 visit will be asked to be followed in the observational period for a total of 96 months from the time of the baseline visit in study B1801023. Once the subject is in the observational period, he or she cannot resume investigational product for the remaining time in the study.
- f. For subjects who agree to participate in the observational period, the first observational visit will occur at the study site and will be scheduled 30 days (± 7 days) after the retreatment early withdrawal visit.
- g. Subsequent observational visits will occur by telephone every 6 months (± 4 weeks) after the first observational visit. For subjects < 18 years of age, telephone contacts will be conducted with the subject's parent or legal representative/guardian. For subjects aged ≥ 18 years, telephone contacts will be conducted with the subject or the subject's parent or legal representative/guardian. The number of telephone contacts will be adjusted based on when the subject enters the observational period.
- h. The final observational visit will occur by telephone contact 96 months (± 4 weeks) after the baseline visit of study B1801023.
- i. Applies to the Month 3 visit.

- j. For subjects in the re-treatment period, the following concomitant medications will be collected: DMARDs, corticosteroids, NSAIDs, and anti-infective agents. Only non-drug treatments received due to an adverse event will be collected.

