- t. Adverse events will be collected from the signing of the informed consent document through 96 months after the baseline visit of study B1801023. For subjects who complete the Month 96 visit in either the active treatment period or the re-treatment period of study B1801023, adverse events will be collected until 30 days after the last dose of investigational product. Events reported as ongoing at the final study 0881A1-3338 visit as well as events starting between the final study 0881A1-3338 visit and the baseline visit of study B1801023 must be recorded on the appropriate eCRF.
- u. For subjects in the withdrawal period, all adverse events including malignancies, serious adverse events, infections, medically important infections (ie, an infection requiring parenteral [IV, IM] anti-infective agent(s) and/or hospitalization), and injection site reactions will be collected.
- v. For subjects in the observational period, only serious adverse events, malignancies and medically important infections (ie, an infection requiring parenteral [IV, IM] anti-infective agent(s) and/or hospitalization), will be collected.

Abbreviations: CHAQ=Childhood Health Assessment Questionnaire; DMARD=Disease-Modifying Antirheumatic Drug; eCRF=electronic Case Report Form; HAQ=Health Assessment Questionnaire; IRB=Internal Review Board; IWR/IVR=interactive web response/interactive voice response; NSAID= Nonsteroidal Anti-inflammatory Drug; PGA=physician's global assessment; TNF=tumor necrosis factor

SCHEDULE OF ACTIVITIES – OBSERVATIONAL PERIOD

For subjects who enter directly into the observational period and do not receive investigational product in study B1801023

The Schedule of Activities table provides an overview of the protocol visits and procedures. Refer to Study Procedures ([Section 6](#)) and Assessments ([Section 7](#)) for detailed information on each procedure and assessment required for compliance with the protocol.

Protocol Activity	Day 1 (Baseline)	Months 6, 12, 18, 24, 30, 36, 42, 48, 54, 60, 66, 72, 78, 84, 90 ^a	Month 96 ^a
	Observational Period		
Informed Consent/Assent	X		
Review inclusion and exclusion criteria	X		
Collect/update contact information	X	X	
Prior and concomitant medications/non-drug treatments ^b	X	X	X
Serious adverse events, malignancies, and medically important infections ^c	X	X	X
Dispense visit reminder card	X	X	
End of Study Subject Summary			X

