6.1.3. Active Treatment Period Follow-up Visit

The follow-up visit will only be completed for subjects who are receiving investigational product in either the active treatment period or the re-treatment period approximately 96 months after the baseline visit in study B1801023. The follow-up visit will occur at the study site 30 days (± 7 days) after the month 96 visit.

The following information will be collected at the follow-up visit:

1. Concomitant medications (DMARDs, corticosteroids, NSAIDs, and anti-infective agents) and non-drug treatments received due to an adverse event.
2. Adverse events, including malignancies, serious adverse events, infections, medically important infections, and injection site reactions.
3. Complete the End of Study Subject Summary CRF.

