8.2. Reporting Period

For SAEs, the active reporting period to Pfizer or its designated representative begins from the time the subject provides informed consent, which is obtained prior to the subject’s participation in the study, ie, prior to undergoing any study-related procedure and/or

receiving investigational product, through at least 96 months after the baseline visit in study B1801023. In addition, for subjects who are either in the active treatment period or the re-treatment period at Month 96, serious adverse events will be collected until 30 days after the last dose of investigational product. SAEs occurring to a subject after the active reporting period has ended should be reported to the Sponsor if the investigator becomes aware of them; at a minimum, all SAEs that the investigator believes have at least a reasonable possibility of being related to investigational product are to be reported to the Sponsor.

AEs (serious and nonserious) should be recorded on the CRF from the time the subject enters either the active treatment period or withdrawal/re-treatment period at the baseline visit of study B1801023 through the subject's last visit in the active treatment period and/or the withdrawal/re-treatment period of the study and for 30 days after the last dose of investigational product for those subjects who are in either the active treatment period or the re-treatment period at Month 96.

For subjects in the active treatment period:

All adverse events (serious and non-serious), including infections, medically important infections, injection site reactions, and malignancy must be recorded on the CRF from the time the informed consent is signed through the Month 96 visit or upon early withdrawal from the study. All adverse events will be collected for the duration of the active treatment period and for 30 days after the last dose of investigational product for those subjects who are either in the active treatment period or the re-treatment period at Month 96.

Events reported as ongoing at the final study 0881A1-3338 visit as well as events starting between the final study 0881A1-3338 visit and baseline visit of study B1801023 must also be recorded on the appropriate CRF.

For subjects in the withdrawal/re-treatment period:

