All adverse events (serious and non-serious), including infections, medically important infections, injection site reactions, and malignancy must be recorded on the CRF from the time the informed consent is signed through the duration of the withdrawal/re-treatment period. All adverse events will be collected for the duration of the withdrawal/re-treatment period and for 30 days after the last dose of investigational product for those subjects who are in either the active treatment period or the re-treatment period at Month 96.

For subjects entering directly into the withdrawal/re-treatment period at the baseline visit of study B1801023, events reported as ongoing at the final study 0881A1-3338 visit as well as events starting between the final study 0881A1-3338 visit and baseline visit of study B1801023 must also be recorded on the appropriate CRF.

For subjects in the observational period:

All serious adverse events (including serious infections), malignancy and medically important infections must be recorded on the CRF from the time the informed consent is signed or when the subject enters the observational period through the Month 96 visit.

For subjects entering into the observational period at the baseline visit of study B1801023, events reported as ongoing at the final study 0881A1-3338 visit as well as events starting between the final study 0881A1-3338 visit and baseline visit of study B1801023 must also be recorded on the appropriate CRF.

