5.2. Treatment-emergent Events

An event is defined as a treatment-emergent event if the event occurred during the active period (either parent or extension studies) or re-treatment period with onset dates between the first dose date of investigational product and within 30 days after the last dose of investigational product. If a treatment-emergent event started in active or re-treatment period and continued to withdrawal or observational period, it will be only counted in active or re-treatment period, it will not be counted in withdrawal or observational period again. If an event started in the withdrawal or observational periods, and after 30 days of the last dose of investigational product of the active period or re-treatment period, this event is not a treatment-emergent event.

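### The re-treatment schedule marks the Follow-up adverse-event cell with the observational-period footnote, so non-serious events in the 30 days after the last dose could be omitted for subjects who complete Month 96 on re-treatment

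*Protocol*

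**What the plan says.** **Re-treatment schedule.** The Follow-up column of the Adverse events row is marked v. Footnote v reads "For subjects in the observational period, only serious adverse events, malignancies and medically important infections". Footnote t, attached to the whole row, says that for Month 96 completers in active treatment or re-treatment "adverse events will be collected until 30 days after the last dose of investigational product". Footnote d limits the Follow-up visit to subjects on investigational product at about Month 96; the visit "will occur at the study site 30 days (± 7 days) after the Month 96 visit".

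**Section 6.1.3.** "The follow-up visit will only be completed for subjects who are receiving investigational product in either the active treatment period or the re-treatment period" at about Month 96. Item 2 lists what is collected: "Adverse events, including malignancies, serious adverse events, infections, medically important infections, and injection site reactions".

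**Section 8.2.** Under the withdrawal/re-treatment heading: "All adverse events will be collected for the duration of the withdrawal/re-treatment period and for 30 days after the last dose of investigational product", the last part applying to those on drug at Month 96.

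**SAP 5.2.** Treatment-emergent events include those with onset "within 30 days after the last dose of investigational product", with the re-treatment period expressly included. SAP 5.6 tabulates them for the full analysis set, active and re-treatment periods pooled.

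**The concern.** The table cell and the text give different instructions on which events to record at one visit. The cell applies a restricted list to subjects who have just finished study drug. Section 6.1.3 applies the full list to the same subjects at the same visit.

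If the cell were followed, three kinds of event could go unrecorded after the last dose: non-serious adverse events, infections that are not medically important, and injection site reactions. SAP 5.2 places that window inside the treatment-emergent period. SAP 5.11 ends exposure at the last dose, so the window can add events to the numerator of the adjusted rate but adds no exposure to its denominator. Any event missed there lowers the rate directly.

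**Working it through.** No planned figure has to be reproduced. The check is a column count, a comparison of provisions and a simple scale calculation.

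**1. Map the marks to the columns.** Each table has 11 columns. Column 8 is Follow-up and columns 9 to 11 are the observational visits.

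| Row | Columns 1–7 | Column 8, Follow-up | Columns 9–11 |
|---|---|---|---|
| Re-treatment, Adverse events | u | v | v, v, v |
| Re-treatment, medications | j (one cell without a letter) | j | k, k, k |
| Active treatment, Adverse events | t | t | u, u, u |

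The re-treatment Adverse events row is 7 + 4 = 11 marks, so Follow-up takes the first v. The active-treatment row is 8 + 3 = 11, and its t is the all-events footnote. The medications row of the re-treatment table gives Follow-up the re-treatment footnote j, so that table does not otherwise treat the column as observational.

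**2. Who attends.** By footnote d and Section 6.1.3, only subjects still on investigational product at about Month 96. None is in the observational period.

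**3. What the other provisions require.** Section 6.1.3 item 2 and the active-treatment schedule ask for all adverse events at this visit. Section 8.2 asks for all adverse events for 30 days after the last dose. Footnote t keeps collection open over the same 30 days. Only the cell marked v points to the restricted list.

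**4. The scope footnotes of the re-treatment table.** Footnote u, used for the on-drug columns, is worded for subjects in the withdrawal period. Footnote v is worded for the observational period. Neither names re-treatment subjects.

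**5. Size of the window.** Section 5.2.2 dispenses no drug at Month 96, and the Month 96 visit itself collects all events, so what is at risk is essentially post-dose time.

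- Per re-treated completer: 30/365.25 = 0.082 subject-years. With the ±7-day visit window: 23/365.25 = 0.063 to 37/365.25 = 0.101. SAP 5.2 stops counting at 30 days after the last dose.
- Number of such completers: not given. Assuming 5 to 30: 5 × 0.0821 = 0.41 to 30 × 0.0821 = 2.46 subject-years.
- Share of a subject's own re-treatment time, assuming 3 to 93 months of 30.4375 days: 30/(3 × 30.4375) = 33% down to 30/(93 × 30.4375) = 1%.
- Scale against the pooled data: if about 100 subjects each contributed 96 weeks in the parent study (assumption), that is 100 × 672/365.25 = 184 subject-years. The window is then 0.41/184 = 0.2% to 2.46/184 = 1.3%, before any extension exposure is added.

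**The case against.** **Other provisions already settle the matter.** Footnote v is limited by its own words to observational subjects, footnote t keeps collection open, Sections 6.1.3 and 8.2 are explicit, and the table calls itself an overview and defers to Section 6. This stands, and it defeats any claim that events will be lost. It does not remove the contradiction. Section 6.1.3 is headed as an active-treatment visit, Section 6.1.2.3 on re-treatment does not mention the visit, and footnote t governs how long events are collected, not which ones. Staff working from the re-treatment material meet the restricted cell first.

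**The letter may be misread.** Superscripts in this table reproduce poorly in the machine-read text: u appears as ii and t as i. The v is distinct and the count fits exactly, so the reading is probable but should be confirmed on the original page.

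**The bias is not confined to one group.** A reader might infer that only re-treated completers are under-counted. The documents do not support that. Subjects who stop active treatment or re-treatment early and enter observation also have only the restricted list collected at their visit 30 days later (Section 6.1.6 item 4; Section 8.2). The SAP pools active treatment and re-treatment and plans no comparison between completers of the two.

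**Conclusion.** The Follow-up cell is wrong as written: it contradicts Section 6.1.3, Section 8.2 and the active-treatment schedule, and sits badly with footnotes d and t of its own table. The consequence is a risk of omission, real only where a site or case report form follows the cell alone. The form is not among the documents.

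Two stronger readings are tempting. One is that on-drug events in the last 30 days of treatment are missed. The window actually lies after the last dose; the SAP merely reports it under its on-drug tables, and few injection site reactions would be expected there. The other is that the primary endpoint is weakened. It is not: malignancy, serious events and medically important infections are collected under either footnote.

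The size is about 0.08 subject-years of collection per re-treated completer. Totals depend on the assumed 5 to 30 completers, and on any of these assumptions the effect on pooled rates is small. The point is worth correcting because it is an operative data-collection rule in a long-term safety study and is almost free to repair.

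**What to change.** In the re-treatment Schedule of Activities, reconcile the Follow-up cell of the Adverse events row with footnote t and Sections 6.1.3 and 8.2 by pointing it to footnote u (all adverse events) instead of v. In the same table, reword footnote u so that it refers to the re-treatment period and not the withdrawal period. Check that the follow-up case report form for re-treated completers accepts all adverse events.

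The cost is one superscript and one footnote term. The visit already takes place at the site and already asks about adverse events. No dose, visit or treatment rule changes, and neither does any SAP definition.

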1. INTRODUCTION

Juvenile idiopathic arthritis (JIA) is the most common autoimmune-autoinflammatory disease in childhood and affects approximately 1 in 1,000 children. Despite advances in diagnosis and treatment options, JIA remains a chronic condition for most affected children. Etanercept is approved by both the US Food and Drug Administration (FDA) and the European Medicines Agency (EMA) to treat pediatric patients with polyarticular JIA aged 2 years and above, who have had an inadequate response to, or who have proved intolerant of, methotrexate. In addition, etanercept is approved by the EMA for use in pediatric patients with severe plaque psoriasis from the ages of 6 to 17 years.

Etanercept binds specifically to tumor necrosis factor (TNF) and blocks its interaction with cell surface TNF receptors. TNF is a naturally occurring cytokine that is involved in normal inflammatory and immune responses. It plays an important role in the inflammatory processes of rheumatoid arthritis (RA), polyarticular JIA, and the resulting joint pathology. Elevated levels of TNF are found in the synovial fluid of RA patients and in both the synovium and psoriatic plaques of patients with psoriatic arthritis.¹

1.1. Indication

Etanercept is a TNF inhibitor that is being developed for the treatment of extended oligoarticular JIA, enthesitis related arthritis (ERA) or psoriatic arthritis (PsA) in pediatric patients.

1.2. Background and Rationale

JIA is a clinically heterogeneous group of several disease types that are characterized by arthritis beginning before the age of 16 years with symptoms persisting for more than 6 weeks. The International League Associations for Rheumatology (ILAR) classification defines 7 distinct subtypes of JIA: systemic arthritis, oligoarthritis (persistent oligoarthritis, extended polyarticular), polyarthritis rheumatoid factor (RF) positive, polyarthritis RF negative, PsA, ERA, and undifferentiated arthritis.

Protocol 0881A1-3338 (B1801014) was designed to assess the clinical benefit and the long-term safety of etanercept for 2 years in pediatric subjects with extended oligoarticular JIA, ERA or PsA. Protocol B1801023 is an 8-year extension study designed to further characterize the long-term safety profile, including malignancy and other serious adverse events, and clinical benefit for those pediatric subjects who received at least one dose of etanercept and completed 96 weeks of investigational product and/or follow-up in study 0881A1-3338.

At the time of the original approved B1801023 protocol, the product label allowed for the use of etanercept in polyarticular JIA, regardless of JIA onset type (refer to the current version of the Summary of Product Characteristics of etanercept for the latest approved indications).² The approval of etanercept in this indication was based on a controlled study which mainly enrolled subjects with polyarticular-onset JIA. Because of the relative paucity of data in other JIA subtypes, this study is being conducted to assess the long-term safety and clinical benefit of etanercept in subjects with extended oligoarticular JIA, ERA, or PsA. In

August 2012, the sponsor was granted approval to extend the indication for JIA to include three new subtypes of the disease and to include long-term safety information for the JIA population, together with reclassification of the licensed indication of polyarticular JIA into the International League of Associations for Rheumatology (ILAR) classification of polyarthritis (rheumatoid factor positive) and polyarthritis (rheumatoid factor negative).

Although the risk-benefit profile of etanercept in JIA has been well characterized, little is known about when or how to discontinue etanercept treatment in patients with JIA after a good clinical response has been achieved, nor are there guidelines from recognized bodies to define criteria for discontinuing treatment of etanercept.³ Thus, the decision to temporarily hold or completely stop therapy is currently a clinical one made between the health care provider and the patient, and is not based on clinical practice guidelines. The criteria for clinically inactive disease in oligoarticular (persistent and extended), polyarticular (RF positive and negative), and systemic JIA have recently been revised by Wallace. Clinically inactive disease is defined as 1) no joints with active arthritis; 2) fever, rash, serositis, splenomegaly, or generalized lymphadenopathy attributable to JIA; 3) erythrocyte sedimentation rate (ESR) or C-reactive protein (CRP) level within normal limits; 4) Physician Global Assessment (PGA) of disease activity score of best possible on scale used; 5) duration of morning stiffness of ≤ 15 minutes; and 6) no active uveitis.⁴

There are some limited data from retrospective studies in the literature regarding discontinuation of etanercept during disease remission. These data provide some support for the concept that etanercept can be withdrawn during remission, and in the event of relapse, restarted with a good clinical response. Remesal et al analyzed the progress of patients with JIA after discontinuation of etanercept and the clinical response to re-introduction of the drug in those who relapsed.⁵ This retrospective chart review of patients between 2004 to 2009 revealed that therapy with etanercept had been discontinued in 26 patients with JIA who had achieved inactive disease using the original definition from Wallace et al for clinically inactive disease.⁶ They note that the majority of patients (69%) relapsed after discontinuation of etanercept, the probability of remaining symptom-free at 6 months was 50%, and the response to re-introduction of treatment was satisfactory. They concluded that etanercept can be discontinued after an “as-yet undetermined period of disease inactivity,” given that even if there is a relapse of disease patients will respond to re-introduction of etanercept. Prince et al found similar results in 9 patients with JIA who experienced relapse after withdrawal of etanercept.⁷ Unlike Remesal et al, they found the period of remission after discontinuation of etanercept was not associated with the duration of inactive disease before the withdrawal of treatment nor the method of withdrawal used (i.e., tapering of treatment versus abrupt cessation), and all 8 patients re-treated with etanercept achieved subsequent remission of disease activity “promptly”. Finally, a retrospective chart review of 171 JIA patients receiving anti-TNF agents, between 1998 and 2009 has recently been reported by Baszis et al.⁸ Of the 171 patients included in the review, 75% received etanercept. Similar to the findings of Prince et al, no correlation between the risk of flare and the length of anti-TNF therapy after inactive disease was achieved was observed in this study. The median time to withdrawal of anti-TNF therapy after inactive disease was achieved was 6.1 months. Of the 136 patients with inactive disease at the time of cessation of TNF treatment, 25% experienced a disease flare within 3 months of the withdrawal of

CCI

Etanercept 0.8 mg/kg once weekly (QW, up to a maximum dose of 50 mg QW) will be studied in this clinical trial. Based on a previous pediatric plaque psoriasis study, which used etanercept 0.8 mg/kg QW (up to a maximum dose of 50 mg QW), this dose was found to have similar pharmacokinetic and safety profiles to etanercept 0.4 mg/kg twice-weekly (BIW, up to a maximum dose of 25 mg BIW), which was used in the pediatric JIA studies. In the pediatric plaque psoriasis study using etanercept 0.8 mg/kg QW (up to a maximum dose of 50 mg QW) and in adult RA studies using etanercept 50 mg QW, etanercept was well tolerated and efficacious. In addition, the etanercept 0.8 mg/kg QW dose is generally more convenient for pediatric patients and their caregivers. In August 2012, the sponsor was granted approval of etanercept dosage regimen of 0.8 mg/kg (up to a maximum of 50 mg per dose) once weekly for the treatment of JIA.

Complete information for etanercept may be found in the Single Reference Safety Document, which for this study is the Investigator's Brochure (IB).

The names, title, address and telephone number(s) of the sponsor's medical expert (Physician Clinician) for the trial is documented in the study contact list in the Study Reference Manual.

